**Achieving Nutritional Adequacy of Vitamins E and K With An Egg/Plant-Based Food Pairing****Executive Summary**

The initial intention of this protocol was to conduct Study 1 and Study 2 as separate investigations, with each study entailing a cross-over design for 4 different 72-h pharmacokinetic (PK) trials. Prior to initiating these plans, the Sponsor provided additional support to conduct an ancillary investigation under *Study 1*, which resulted in a total of 6 different 72-h PK trials; no changes were made to *Study 2* (*i.e.*, 4 PK trials). If participants consented separately to complete both Study 1 and Study 2, this resulted in a total of 10 PK trials. Both during and post-pandemic, our progress to conduct and complete Study 1 and 2 has been impacted. Thus, this revised protocol (submitted Aug 2022) reflects our efforts to gain efficiency in our work and address the study's primary objectives by combining a subset of Study 1 and Study 2 PK trials into a new Study 3 that only involves 6 PK trials. Our intent here is to complete all procedures in participants who are actively involved in *Study 1* and *Study 2*. Those who complete *Study 1* will be invited to reconsent for enrollment in *Study 2*. Thereafter, no new participants will be enrolled in *Study 1* or *Study 2*; all future participants will be enrolled only in *Study 3*. With this plan, we will enroll 5 participants in *Study 1* to ensure fulfillment of primary and ancillary objectives. A maximum of 5 persons will complete *Study 2* and up to 10 participants will complete *Study 3*. Thus, total enrollment across Study 1, 2, and 3 ( $n =$  up to 20) does not increase the number of total participants targeted for enrollment compared with our initial protocol that only involved *Study 1* and *Study 2*. We can therefore achieve study all objectives without increasing overall enrollment, but will be able to reduce participant burden and potential risk.

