#### A. Research Design

Our initial objective was to conduct two separate trials having  $1 \times 4$  study designs (Study 1 (4-arms) & Study 2 (4-arms). Arms 5 and 6 in Study 1 were added to address a secondary objective through an ancillary study. Due to the significant delay in progress caused by the global pandemic, we plan focus the remainder of work on the primary objectives by enrolling only 5 participants, instead of 10, for Study 1 and create a new Study 3 that combines select arms of Study 1 and Study 2 into a succinct  $1 \times 6$  study design. This will avoid the need to re-consent persons to complete Study 2 and overall reduce participant burden.

For the planned studies, we will conduct three separate cross-over studies. The first study consists of a 6-arm cross-over study (Study 1), the second in a separate cohort will be 4-arm crossover study (Study 2), and the third study consists of a 6-arm cross-over study (Study 3). For all studies, healthy adults who fulfill the enrollment criteria will be enrolled from the Columbus, OH area. Studies will be completed in the OSU Human Nutrition Research Center.

For *Study 1*, fasted participants will ingest  $\sim 100$  g of deuterium-labeled steamed spinach with 0, 1, 2, or 3 hardboiled eggs (Study 1 Arms 1-4, respectively). In Study Arm 5, participants will ingest spinach alone followed by 1 egg 3-hours later. In Study Arm 6, participants will ingest spinach with 1 egg followed by another egg 3-hours later. Thus, Study Arms 1-4 will test the dose-dependent effects of eggs on nutrient bioavailability and Study Arms 5-6 (with comparison to Study Arms 1 and 2) will test the ‘timing’-dependent effects of eggs on nutrient bioavailability. For all studies,  $\sim 100$  g of deuterium-labeled steamed spinach (to provide 2 mg  $\alpha$ -T and 500  $\mu$ g PQ) will be administered. Hardboiled eggs will be administered at a dose of 0-3 eggs ( $\sim 50$  g each) to provide 0-14.4 g fat. For each cross-over trial, blood will be collected prior to (0 h) and at 3, 4.5, 6, 7.5, 9, 12, 24, 36, 48, and 72 h post-test meal ingestion to ensure that blood samples are collected at times corresponding to the  $T_{max}$  of  $\alpha$ -T between 10-12 h and  $T_{max}$  of PQ at either 3-5 h or 6-8 h. Plasma and chylomicrons will be collected and archived as we described.

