For *Study 2*, a separate cohort of healthy adult participants will ingest  $\sim 100$  g of deuterium-labeled steamed spinach alone (0 g fat), or with 2 egg whites (0 g fat), 2 whole eggs (9.6 g fat), or vegetable oil (9.6 g fat) (Study 2 Arms 1-4, respectively). Blood will be collected from 0-72 h as indicated above, processed, and archived until analyzed.

For *Study 3*, a separate cohort of healthy adult participants will ingest  $\sim 100$  g of deuterium-labeled steamed spinach alone (0 g fat), or 1, 2, or 3 hardboiled eggs (Study 1 Arms 1-4), or with 2 egg whites (0 g fat), or vegetable oil (9.6 g fat) (Study 2 Arms 2 & 4). Blood will be collected from 0-72 h as indicated above, processed, and archived until analyzed.

For each study, a 7-d washout period between study arms is sufficient, based on our reports, to fully eliminate labeled compounds and prevent “carry-over” to the subsequent trial. To standardize postprandial responses and accurately define pharmacokinetic parameters under *Studies 1-3*, all foods will be controlled for 3-d preceding each trial and for the initial 24-h of each trial. The controlled diet will be eucaloric and standardized for  $\alpha$ -T and PQ intakes. For all of these planned studies, only blood will be collected for the isolation of plasma and chylomicrons. No fecal samples, urine samples, or genetic material is being collected.

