## B. Sample

**Total Number of Participants For Studies 1-3.** For both planned studies, up to 40 persons in total will be screened in order to identify 15 persons (n = 5 per study) who meet the below inclusion/exclusion criteria. 10 persons in each study are needed to enhance statistical power and consider potential effects due to gender as described below. The newly added Study 3 will allow us to still have 10 persons under the arms that fulfill the primary objectives. Maximum 15 persons will be formally enrolled in the study.

**Inclusion/Exclusion Criteria.** Participants (18-65 y) will be required to meet the following **inclusion criteria:** a) BMI = 19-25 kg/m^2; b) normolipidemic (total cholesterol <240 mg/dL; triglyceride <150 mg/dL); c) glucose <100 mg/dL; d) normal hematocrit level (41%-50% for men and 36%-48% for women); e) normal hemoglobin level (13.5-17.5 g/dL for men and 12.0-15.5 g/dL for women); f) no use of dietary supplements for >1 mo; g) no use of medications that affect lipid or glucose metabolism; h) non-smoker; and i) no history of gastrointestinal disorders. Participants having any of these criteria will be **excluded:** a) egg allergy; b) >2 alcoholic drinks/d; c) >7 h/wk of aerobic activity; d) >2 kg body mass change in the past 1 mo; e) women who are pregnant, lactating, or initiated or changed birth control in the past 3 mo, f) history of iron deficiency anemia; g) vegetarian. We will also not enroll any participants using any medications to manage diabetes, hypertension, or hyperlipidemia (e.g. statins, metformin, ACE inhibitors) or any blood thinning medications [Warfarin]).

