**Power Calculation.** The quantity of egg-derived fat is similar to that in our report demonstrating a dose-response increase in d6- $\alpha$ -T bioavailability when ingested with 0-11 g of fat derived from cream cheese. Using the smallest difference in d6- $\alpha$ -T Cmax, which occurred between the 0 g and 2.4 g fat levels (**Fig 2A**), our power analysis indicated that only 5 participants would be needed to detect statistically significant differences (90% power, P<0.05; PS Power and Sample Size). Similar powering is also obtained when using d6- $\alpha$ -T AUC0-72 h or absorption (%). Studying so few participants is impractical for establishing dietary recommendations. Thus, for studies 1-3 separate cohorts of 5 adults will be enrolled. By combining participants from all 3 studies, we will have 10 adults under each primary objectives to consider egg-dependent increases in **primary outcomes** (Cmax, AUC, estimated absorption of  $\alpha$ -T or PQ). This increases statistical power to >97% (P<0.01) while allowing for consideration of potential differences between men and women.

**Recruitment.** We will recruit participants through posted flyers, e-mail, electronic and newsprint advertisements (e.g. campus student and faculty/staff newspapers, local and regional newspapers), word of mouth, and social media (e.g. Facebook). The posted advertisements will instruct interested participants to complete an online eligibility survey or call the study center ([name] Laboratory, Department of Human Sciences) to obtain further information. During the phone-in hours, a trained individual (i.e. project coordinator or graduate assistant) will be available to describe the study and determine preliminary qualification by conducting a scripted phone interview (e.g. do you take dietary supplements?, do you smoke?; see *Phone Script* attachment). The individual will record answers and assess whether or not the person calling is likely or not to be an acceptable study participant. If the caller and the interviewer agree that the caller should participate, the prospective participant will be invited to a screening meeting, where the study will be fully described and the individual will be provided a consent form to complete prior to any

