#### **D. Detailed Study Procedures**

**Overview of Study Procedures.** Potential participants who call the study center in an anonymous manner for more information will be given a brief description about the study and asked a few questions to determine their eligibility (see *Phone Script* attachment). If they meet the eligible criteria, they will be invited to the study center for a screening meeting. During the meeting, the Informed Consent (see *Informed Consent* attachment) will be explained and provided for them to review. The participant will then be given the opportunity to review the Informed Consent form. If he/she chooses to participate in the study, they will then be asked to provide written consent. After receiving informed consent, the participants' height, weight, waist circumference, and blood pressure will be measured. Additionally, a small fasting blood sample will be collected to blood chemistry analysis. If they are not fasted at least 10 hours), they will be asked to come back in the fasted state at time of mutual convenience. These blood results in combination with anthropometric parameters will determine the participant's eligibility. Eligible participants who agree to proceed with the study will then be formally enrolled to complete one of the three planned cross-over studies (i.e. Study 1 or Study 3 with 6 cross-over periods; or Study 2 with 4 cross-over periods). Participants may complete both cross-over trials provided that they wash-out between studies for >6 weeks. We estimate that all procedures to complete Study 1 and Study 3 will require ~12 weeks per participant and that Study 2 will require ~8 weeks per participant.

**Screening Meeting.** Potential participants who have met the initial criteria of the study (based on the telephone interview) will be invited to the study center at a mutually convenient time. During

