Cover Page

Document: Statistical Analysis Plan

Official Study Title: Achieving Nutritional Adequacy Of Vitamin E With An Egg/Plant-Based Food Pairing

ClinicalTrials.gov ID: NCT04287816

Document Date: 10/01/2025

Statistical Analysis Plan

Power Analysis & Sample Size Determination. Plasma deuterium labeled (d_x) α -tocopherol (α -T) area under the curve from 0 to 72 hours (AUC_{0-72}) was the primary outcome and formed the basis for power analysis. Sample size estimates were derived from a previously published study demonstrating a dose-dependent increase in d_6 - α -T bioavailability with 0–11 g of fat from cream cheese.¹ Using the smallest observed difference in d_6 - α -T AUC_{0-72} —between the 0 g and 2.4 g fat trials—power analysis indicated that a sample size of 5 participants would be sufficient to detect statistically significant differences (90% power, $\alpha = 0.05$; PS Power and Sample Size).

All data (means \pm SE) were analyzed using GraphPad Prism (version 10, GraphPad Software, LLC). Variance was assessed using the Brown–Forsythe test, and data were log-transformed when necessary to meet assumptions of equal variance prior to statistical testing.

Predefined between-treatment comparisons included:

1. Dose-dependent effect of eggs on d_x - α -T pharmacokinetics: SPINACH, SPINACH + 1 EGG_{0 h}, SPINACH + 2 EGGS_{0 h} and SPINACH + 3 EGGS_{0 h}
2. Food matrix effects on d_x - α -T pharmacokinetics: SPINACH + 2 EGGS_{0 h}, SPINACH + WHITE and SPINACH + OIL
3. Meal timing effects on d_x - α -T pharmacokinetics: SPINACH, SPINACH + 1 EGG_{0 h}, SPINACH + EGG_{3 h}, and SPINACH + EGGS_{0 & 3 h}.

Dose-dependent and matrix effect comparisons, which formed the primary objective of the study, were analyzed together using one-way repeated measures analysis of variance (ANOVA), or linear mixed-effects models (LMM) in cases of missing data, followed by Holm–Šidák post hoc tests when a significant main effect was observed ($p < 0.05$).

The meal timing effect, which was the exploratory objective, was analyzed separately using repeated measures ANOVA or LMM in cases of missing data, followed by Fisher’s least significant difference (LSD) test when a main effect was significant ($p < 0.05$).

Reference

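### Does the missing subject unit, study term and duplicate-record rule undermine the combined dose and matrix analysis?

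*SAP*

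**What the plan says.** The SAP lists three sets of comparisons. The dose set (SPINACH and SPINACH with 1, 2 or 3 eggs) and the matrix set (2 EGGS, WHITE, OIL) form the primary objective and "were analyzed together using one-way repeated measures analysis of variance (ANOVA), or linear mixed-effects models (LMM) in cases of missing data", followed by Holm–Šidák tests. Treatment is the only factor named. The data analysis paragraph in Protocol section III.B is no fuller on subject unit, study or duplicates.

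Combining the studies comes from the protocol's Power Calculation: "By combining participants from all 3 studies, we will have 10 adults under each primary objectives". The arm table in section I shows that only Study 3 has all six primary arms. Study 1 lacks WHITE and OIL, and Study 2 lacks 1 EGG and 3 EGGS. SPINACH and 2 EGGS occur in all three.

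On who is in which study the protocol speaks two ways. The Executive Summary says that Study 1 completers "will be invited to reconsent for enrollment in" Study 2, and section III.D adds: "Participants may complete both cross-over trials provided that they wash-out between studies for >6 weeks". Section III.A describes "the second in a separate cohort will be 4-arm crossover study (Study 2", and for both Study 2 and Study 3 says that "a separate cohort of healthy adult participants will ingest" the test meals. On numbers, the Executive Summary has "up to 10 participants will complete" Study 3, while section III.B has "15 persons (n = 5 per study".

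**The concern.** A person who completes Study 1 and then Study 2 has 1 EGG and 3 EGGS only in the earlier study, WHITE and OIL only in the later one, and SPINACH and 2 EGGS in both. If that person is one subject in a treatment-only model, some treatment contrasts are partly contrasts between studies more than six weeks apart. Anything that moves AUC between the studies (spinach lot, assay batch, season) then leaks into the treatment estimate.

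The contrast most exposed in practice is 2 EGGS v OIL. The two meals are matched at 9.6 g fat, so the true difference could be small, and the contrast carries the Study 2 hypothesis that egg lipid outperforms vegetable oil. A reader also cannot rebuild the primary estimates without knowing which records went in.

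**Working it through.** **The plan's own figure.** Ten adults per objective follows from 5 per study: the dose arms have 5 (Study 1) + 5 (Study 3) = 10, and the matrix arms have 5 (Study 2) + 5 (Study 3) = 10.

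**Which contrasts can be affected.** The dose list gives 6 pairs and the matrix list 3, so 9 in all. Let d be a shift in ln(AUC) added to every Study 2 record. Study 3 people supply all six arms, so a shift between Study 3 and the other studies cancels within person. Only a Study 1-to-2 shift within the same person matters. SPINACH v 2 EGGS, 1 v 3 EGGS and WHITE v OIL are unaffected. The other six pairs can be.

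**Person as subject, all 5 continuing, 5 in Study 3.** Each contrast is an average over 10 people, 5 of whom can carry the shift.
- Study 1 copies only: 2 EGGS v OIL and v WHITE are biased by 5d/10 = 0.50d, and the dose pairs by 0.
- Study 2 copies only: the four affected dose pairs are biased by 0.50d, and the matrix pairs by 0.
- Copies averaged: all six are biased by 5 × 0.5d/10 = 0.25d. Keeping both as separate rows gives 0.23d to 0.27d.

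**Other cases the documents allow.**
- 5 continuing, 10 in Study 3: 5d/15 = 0.33d with one copy, 0.17d with both.
- 3 of 5 continuing, 5 in Study 3: 3d/8 = 0.375d (Study 1 copies, matrix pairs), 3d/10 = 0.30d (Study 2 copies, dose pairs), about 0.15d to 0.20d with both.
- 3 of 5 continuing, 10 in Study 3, both kept: 0.10d to 0.12d.
- No Study 2 participants: 0.

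**Person-within-study as subject.** With a random intercept and an assumed intraclass correlation of 0.7 to 0.3, the 5-continuing, 5-in-Study-3 case leaves 0.02d to 0.08d for 2 EGGS v OIL and 0.04d to 0.14d for 2 EGGS v 1 EGG. Three separate cohorts of 5 give the same values. The other overlap cases go down to about 0.01d. With fixed person-by-study blocks the bias is 0 in all nine pairs.

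**Size of d.** No document gives it. The protocol's ±3% (Pitfalls and Alternatives) is expected variability in the spinach dose. Reading it as a shift means placing all of Study 1 at one extreme and all of Study 2 at the other, with AUC proportional to dose: d = ln(1.03/0.97) = 0.060. Over assumed shifts of 3% to 20%, the bias at 0.25d to 0.50d runs from 0.25 × 3% = 0.75% to 0.50 × 20% = 10%.

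**Would an explicit block help?** For 2 EGGS v OIL, with 5 continuing and 5 in Study 3, take d = 0.06 and an assumed within-person log-SD s. Mean squared error is bias² + variance.

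| Handling | Bias | Variance | s = 0.14 | s = 0.20 |
|---|---|---|---|---|
| Person, Study 1 copy only | 0.030 | 0.200s² | 0.0009 + 0.00392 = 0.00482 | 0.0009 + 0.0080 = 0.0089 |
| Person, both copies | 0.015 | 0.168s² | 0.000225 + 0.00329 = 0.00352 | 0.000225 + 0.00672 = 0.00695 |
| Fixed person-by-study blocks | 0 | 0.177s² | 0.00347 | 0.00708 |

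Against keeping both copies, the block gains about 1% at s = 0.14 and loses about 2% at s = 0.20. The two break even where (0.25d)² = 0.009s², so d = 0.38s, or about 0.05 to 0.08. With both copies kept, 95% interval coverage at d = 0.06 is 94.2% (s = 0.14) or 94.6% (s = 0.20). With Study 1 copies alone it is 92.4% or 93.8%.

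**The case for a change.** The best case for a change is that the omission is real and sits in the primary analysis, that d is unknown, and that a few sentences would settle it. The dose tolerance cannot cap d. Assay variation (CV under 6%), the gap between studies, and the fallback of standardising portions to PQ (which frees the α-T dose) could each add to it. At an assumed d of 0.20 the single-copy bias for 2 EGGS v OIL would be 0.10 on the log scale, and a block would then clearly be better. The SPINACH and 2-EGG records needed to remove the shift are already planned in both studies.

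The omissions and the unknown size of d stand. The inference to a faulty analysis does not. The 0.50d figure needs the person as subject, all five continuing, exactly five in Study 3, and one copy of each duplicate thrown away. No passage says that a copy is discarded. Completers are only invited, and the number who accept is not given. On dose, each pooled lot is assayed and portioned to about 2 mg α-T, which works towards a small shift. The limit of 10 in Study 3 is a ceiling, so 5 there is not in conflict with it.

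**Conclusion.** The concern does not call for a change. The SAP leaves out detail, but no rule it states gives a wrong answer. Laying out the combined data with one row for each person in each study leaves arms empty for everyone outside Study 3. That is missing data, for which the SAP already names a mixed model, and the bias is then about 0.01d to 0.14d: under 1% at d = 0.06 (0.14 × 0.06 = 0.0084) and under 3% even at d = 0.20 (0.14 × 0.20 = 0.028). Keeping both copies with the person as subject gives about 0.10d to 0.27d and, at d = 0.06, practically the same mean squared error as a fully blocked model. Blocking has a clear advantage only over discarding a copy, or if d is well above about 0.05 to 0.08.

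This rests on assumed values of d, log-SD (0.14 and 0.20) and intraclass correlation (0.3 to 0.7), and on 3 to 5 of 5 continuing with 5 to 10 in Study 3. The separate-cohort wording in sections III.A and III.B disagrees with the re-enrolment allowed in the Executive Summary and section III.D. Those passages must be reconciled, but the slip is clerical, and reporting how many people took each route resolves it.

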**I. Objectives**

The objective of this study is to use deuterium-labeled spinach (containing stable isotopes of vitamin E ( $\alpha$ -tocopherol;  $\alpha$ -T) and vitamin K (phylloquinone; PQ)) to validate eggs as a dietary tool to improve  $\alpha$ -T and PQ bioavailability directly from a model plant food, and hence achieve nutrient adequacy. Our hypothesis is that the bioavailability of  $\alpha$ -T and PQ from deuterium-labeled spinach will be potentiated by egg intake in a dose- and time-dependent manner by increasing their secretion in intestinal-derived chylomicrons. Further, phospholipid-rich egg yolk lipid will enhance nutrient bioavailability compared with vegetable oil. To test this, our team with expertise in bionutrition, plant sciences, and advanced mass spectrometry will fulfill these specific aims:

- 1) Study 1: Assess egg-mediated improvements in  $\alpha$ T and PQ bioavailability

The working hypothesis is that, compared with deuterium-labeled spinach alone, co-ingestion of eggs will dose- and time-dependently increase plasma bioavailability of spinach-derived deuterium-labeled  $\alpha$ T and PQ (based on  $AUC_{0-72\text{ h}}$ ,  $C_{\max}$ , and % estimated absorption) without affecting time to maximal concentrations or half-lives. Further, eggs will dose-dependently improve chylomicron enrichment of deuterium-labeled  $\alpha$ T and PQ in association with their greater absorption.

- 2) Study 2: Potentiation of  $\alpha$ -T and PQ bioavailability by egg yolk lipid

The *working hypothesis* is that phospholipid-rich whole eggs will enhance spinach-derived  $\alpha$ T and PQ bioavailability compared with vegetable oil, and will be most functionally responsible for the benefits of eggs to enhance lipophilic nutrient absorption. We further hypothesize that egg whites will more greatly promote spinach-derived nutrient bioaccessibility compared with spinach alone.

### 3) Study 3: Combination of primary objectives in Study 1 and 2

This newly added Study 3 consists of select trials from *Study 1* and *Study 2* to allow us to assess dose-dependent effects of eggs and food matrix-dependent effects in a succinct study design involving only 6 pharmacokinetic trials.

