**Deuterium-labeled Plants: A Tool for Evaluating Nutrient Bioavailability.** The food matrix, nutrient quantity, and other determinants of bioavailability have been examined in humans and animals. However, research tools have evolved in their sophistication to better interpret experimental outcomes. For example, when eggs were co-ingested with a mixed-vegetable salad, there was insufficient sensitivity to detect a dose-response effect of eggs (75 g vs 150 g) on  $\alpha$ -T absorption. The use of unlabeled  $\alpha$ -T also precluded a determination of which food source(s) accounted for the increase in  $\alpha$ -T absorption, which was further confounded by endogenous  $\alpha$ -T that is detectable in intestinal- and liver-derived chylomicrons and VLDL, respectively. Thus, an accurate measure of the proportion of the orally administered  $\alpha$ -T that was absorbed and available for target tissue delivery could not be quantified. To address these limitations, the [name] Lab and others use non-radioactive or stable isotopes of  $\alpha$ -T and PQ to assess bioavailability in a scientifically rigorous manner. These tools enable precise nutrient assessments in plasma and isolated lipoproteins using LC-MS and detailed pharmacokinetic analyses to define gut-to-liver nutrient trafficking. Notable examples demonstrating this expertise of [name] (PI) include studies examining cigarette smoke-induced oxidative stress on dietary  $\alpha$ T requirements, vitamin C interactions that improve  $\alpha$ -T status, the detriment of metabolic syndrome on gut-to-liver trafficking of  $\alpha$ -T, and the dose-response effect of dietary fat on  $\alpha$ -T absorption (Fig 2).

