We provided the most accurate evidence in humans that  $\alpha$ -T absorption, when administered in an apple matrix, is only 10% when ingested in the absence of fat, and that its absorption increases in a dietary fat-dependent manner up to 33% when co-ingested with 11 g of fat (Fig 2). Pharmacokinetic analysis indicated that the time to maximal plasma concentrations of  $\alpha$ T ( $T_{max}$ ) and its half-life ( $t_{1/2}$ ) were unaffected regardless of the quantity of dietary fat ingested. Higher maximal concentrations ( $C_{max}$ ) of  $\alpha$ -T in response to increasing dietary fat (Fig 2) were therefore attributed to greater intestinal absorption rather than altered gastric emptying. We also observed that fat intakes, within the range of 0-11 g ingested, linearly increased  $\alpha$ -T bioavailability such that 0.43 mg of  $\alpha$ -T was absorbed for each additional gram of fat ingested (Fig 2C). Thus, our planned studies will exploit the highly digestible lipid content of eggs (4.8 g total fat/egg) to demonstrate that eggs dose- and time-dependently improve plant-derived  $\alpha$ T and PQ bioavailability, and more substantially than phospholipid-free vegetable oil. Further, because co-PI [name] is enlisted to hydroponically grow deuterium-labeled spinach, pharmacokinetic responses of both deuterium-labeled  $\alpha$ -T and PQ can be assessed independently of the confounding effects of the low-level amounts of unlabeled  $\alpha$ -T and PQ present in egg yolks or those already present in intestinal or liver tissue.

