involvement in the study procedures. Data collected during this phase will include participant's age, health status, physical activity, and contact information (see *Informed Consent* attachment).

**Anticipated Data Analysis Plan.** Primary outcomes ( $C_{\max}$ ,  $AUC_{0-72\text{ h}}$ , absorption) will be analyzed initially using 2-way repeated measures ANOVA to assess effects due to treatment, gender, and their interaction. If no gender effects are observed, consistent with prior reports, we will reassess outcomes using 1-way RM ANOVA and Bonferroni's post-test, as appropriate, to focus on egg-dependent effects on pharmacokinetics. Multiple linear regression, controlling for within-subject repeated measures, also will be performed to define relations among study variables.

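### A dose-dependent egg effect is part of the primary objective, but the SAP neither tests nor estimates a dose gradient

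*SAP*

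**What the plan says.** The SAP lists three predefined comparisons: egg dose (spinach with 0, 1, 2 or 3 eggs at time 0), food matrix (2 eggs, egg white, oil) and meal timing. Dose and matrix together form the primary objective. They are analysed jointly by one-way repeated-measures ANOVA, or by a linear mixed model if data are missing, "followed by Holm–Šidák post hoc tests when a significant main effect was observed". The SAP names no trend test, no linear contrast and no term for egg number or grams of fat.

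The Protocol frames dose as an ordered question:

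- I. Objectives, Study 1: "co-ingestion of eggs will dose- and time-dependently increase plasma bioavailability", relative to spinach alone.
- II. Background and Rationale, on the earlier apple and cream-cheese study: "fat intakes, within the range of 0-11 g ingested, linearly increased" α-tocopherol bioavailability. The same section gives 4.8 g fat per egg.
- II, Anticipated Results: the amount of egg lipid is expected to predict the bioavailability parameters at P<0.05.
- III.B, Anticipated Data Analysis Plan: one-way repeated-measures ANOVA with Bonferroni tests. In addition: "Multiple linear regression, controlling for within-subject repeated measures", to describe relationships among variables.

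The SAP does not mention the regression.

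**The concern.** The four time-0 arms are equally spaced (0, 4.8, 9.6 and 14.4 g fat) and the hypothesis is directional. The natural test asks whether the response rises with egg number, and the natural estimate is a slope per egg. The SAP supplies neither.

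Two consequences follow. First, the omnibus F covers all six dose and matrix conditions and treats them as unordered labels. An effect of oil alone can make it significant, so it cannot by itself support a statement about eggs. Second, the dose claim must be read from which adjusted pairs reach significance. A mixed pattern, such as 0 vs 3 significant but 0 vs 1 and 1 vs 2 not, has no agreed reading as dose dependence and gives no size per egg. The Protocol's prediction about egg lipid is left without an analysis in the SAP.

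**Working it through.** **The plan's own figure.** The Protocol says "our power analysis indicated that only 5 participants would be needed to detect statistically significant differences", based on the smallest difference, "which occurred between the 0 g and 2.4 g fat levels"; the SAP repeats this for AUC. Neither document gives the difference or its SD, so the 5 can be neither reproduced nor refuted. Solved backwards, a two-sided paired t test with n=5, 90% power and α=0.05 needs a standardised paired difference of about 1.97. That value gives 99.2% power at n=10 and α=0.01, which agrees with the Protocol's statement of more than 97%.

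**Assumptions for the comparison.** Complete six-arm data, compound symmetry and log-scale analysis. Log means are 0, b, 2b, 3b for 0 to 3 eggs with b = ln 1.10 = 0.0953; egg white = 0 and oil = 2b. Residual log-SD σ is 0.15 (n=5), 0.20 (n=10) or 0.25 (n=10). The gain and the SDs are assumptions; the documents give neither.

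**Linear contrast** (scores −3, −1, 1, 3; sum of squares 20). The contrast of means is −3(0) − b + 2b + 3(3b) = 10b = 0.953. The noncentrality is 10b / (σ√(20/n)), with 5(n−1) error df:
- n=5, σ=0.15: 0.953/(0.15×2.000) = 3.18; power 86%
- n=10, σ=0.20: 0.953/(0.20×1.414) = 3.37; power 91%
- n=10, σ=0.25: 0.953/(0.25×1.414) = 2.70; power 75%

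**Omnibus F over six arms.** λ = nΣ(μ−μ̄)²/σ². For (0, 1, 2, 3, 0, 2)b the sum is (18 − 8²/6)b² = 7.333b² = 0.0666, so λ = 14.8, 16.7 and 10.7. Power is 74%, 86% and 65% by formula, and 73%, 86% and 64% by simulation.

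**Holm–Šidák run only after a significant F** (6,000 simulated trials per setting, 15 pairs):

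| Setting | Linear contrast | Omnibus F | Any dose pair | 0 vs 3 eggs | All three adjacent steps |
|---|---|---|---|---|---|
| n=5, 0.15 | 86% | 73% | 46% | 41% | about 0% |
| n=10, 0.20 | 91% | 86% | 61% | 56% | about 0% |
| n=10, 0.25 | 75% | 64% | 37% | 31% | about 0% |

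Restricting to the 9 pairs within the dose and matrix sets (6 + 3) raises 0 vs 3 eggs to about 49%, 62% and 37%.

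**Oil-only effect.** Set every arm equal except oil, which is raised by e. Then Σ(μ−μ̄)² = (5/6)e². For an assumed 50% rise, e = ln 1.5 = 0.405 and λ = 30.4, 34.2 and 21.9. The F is significant in about 98%, more than 99% and 95% of trials although eggs do nothing. With a 21% rise (e = 2b) the figures are 38%, 48% and 31%. In the 50% scenario the Holm–Šidák step declares a false dose pair in only about 2–3% of trials, so the problem lies in reading the F as dose evidence, not in the error control of the pairs.

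**Larger effects from the documents.** The background reports absorption of 10% without fat and 33% with 11 g. Interpolating, (33−10)/11 × 4.8 = 10.0 points per egg, hence about 10, 20, 30 and 40% for 0 to 3 eggs. The last value is an extrapolation, because 14.4 g exceeds 11 g. The first step is ln 2 ≈ 0.69, against 0.095 above. With these means the contrast, the F and the 0-vs-3 test all have about 100% power in the three settings, and all three adjacent steps are significant in roughly 40–73% of trials. If each egg step equals the implied planning effect (about 1.97 paired SDs), the overall tests again reach about 100%. All three steps then appear in about 80% (n=5) and 99.8% (n=10).

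**The case against.** The strongest reply is that the power loss comes from the assumed 10% per egg. The figures in the Protocol's background suggest a far larger effect, at which nothing is lost in the overall tests. This stands: a reader might infer that the SAP's method is generally low-powered, and the documents do not support that. They also do not exclude a modest effect, since the planning data come from cream-cheese fat with fortified apples, not eggs with spinach.

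It is also fair that the omnibus F itself loses only about 5–13 points in the settings above. The large gap appears against multiplicity-adjusted pairs, which answer a narrower question, and the contrast was not charged for multiplicity.

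A reader might further infer that the planned analysis cannot show a gradient. That is too strong: significant ordered adjacent steps would show one, and at the larger effects they often appear. Nor did the SAP abandon a declared dose test. The Protocol's regression has no stated role as the dose test, and its treatment comparison was already an ANOVA with pairwise tests.

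The Protocol's remark on the earlier egg study, "there was insufficient sensitivity to detect a dose-response effect of eggs", concerns research tools and unlabelled tocopherol. It does not show that this trial will repeat that result.

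Finally, the contrast is not uniformly better. With a plateau after one egg (n=10, σ=0.20, step 0.2 on the log scale, oil also raised by 0.2) it has about 56% power against 76% for the F, though any dose pair is significant in only about 41%. A significant contrast also does not prove that each added egg helps.

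**Conclusion.** The concern holds as a gap between objective and analysis. A stated, ordered dose hypothesis within the primary objective has no dose test and no slope estimate, and the omnibus test mixes in two arms that are not whole-egg doses. This follows from the text and depends on no effect size.

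The power cost is conditional. At 10% per egg, the contrast exceeds the chance of any significant dose pair by 40, 30 and 38 points (86−46, 91−61, 75−37), and exceeds the omnibus F by 13, 5 and 11 points. At the effects implied by the background or by the planning figure, the loss in the overall tests is nil. Without an egg-specific difference and SD, the documents do not settle which case applies.

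All figures assume complete six-arm data. By design, Study 1 lacks the egg-white and oil arms and Study 2 lacks the 1-egg and 3-egg arms, so exact power will differ.

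**What to change.** In the same repeated-measures model or mixed model:

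- Make the dose test a 1-df linear contrast over the four time-0 arms (0, 1, 2, 3 eggs; scores −3, −1, 1, 3), not conditional on the omnibus F.
- Report the slope per egg with a 95% CI.
- Check departure from linearity, for example with the quadratic term. Three eggs (14.4 g fat) lie beyond the 0–11 g range reported as linear.
- Keep the Holm–Šidák pairs for specific steps and for the matrix effects. State which pairs form the family and whether the contrast shares its α with them.
- State what became of the Protocol's regression.

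The SAP is dated 10/01/2025 and written in the past tense. If outcome data had been seen before the contrast is added, label it post hoc and tie it to the Protocol's prediction about egg lipid.

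The cost is a few lines of text and one contrast. The downside is lower power than the omnibus F if the response plateaus after one egg; the retained tests and the linearity check cover that.
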